Functionally-tailored Oral Care Intervention for Community-dwelling Older Adults With Dementia and Their Caregivers Study title:

Identifiers: NCT04238520

Document date: 02-17-2023

I. Purpose

The purpose of this project is to develop and validate an oral care intervention to support community-dwelling older adults with dementia and their family caregivers (FCG).

II. Research Team

Table 1 Providers and roles

III. Project Overview

Persons with dementia (PWD) gradually lose their ability to perform oral self-care, leading to poor oral hygiene. Poor oral hygiene increases the risk of dental caries, periodontal disease and other oral pathologies, and initiates a cascade of oral health decline among PWD, which in turn may accelerate cognitive decline. Importantly, these changes often begin before nursing home (NH) placement. Besides pain and discomfort, poor oral health can lead to agitation and delirium and increase caregiver (CG) stress. It can also affect quality of life, cause malnutrition, increase insulin resistance, and lead to aspiration pneumonia, cardiovascular complications, and other life-threatening conditions in these vulnerable individuals. Early intervention is essential to stop/slow down the oral health decline and its cognitive/systemic impacts in PWD.

Existing oral hygiene interventions have demonstrated efficacy in improving oral health, reducing aspiration pneumonia and even slowing down cognitive decline. However, these programs were designed for NH residents and are not tailored for the great majority of PWD who reside in the community. As such, they fail to account for the reciprocal physical and emotional relationship between the PWD and their family caregivers and its influence on oral care. Furthermore, although oral hygiene education is a standard component of dementia dental care, it is usually not tailored to each patient's level of oral self-care function. In response to these gaps, we propose a study to develop and evaluate a functionally-tailored oral hygiene intervention to improve oral health for community-dwelling PWD while reducing caregiver burdens and improving care partner relationships.

The study consists of two phases corresponding to two aims. For Aim 1 we will develop a modularized, functionally-tailored oral care intervention based on literature review and CG interview input. We anticipate eight training modules that can be used alone or in varying combinations to provide functionally-appropriate oral care rehabilitation for PWD and needbased skills training to their family CGs. These will be adapted from Mouth Care Without a Battle, a validated oral hygiene intervention developed for NH residents with dementia. Aim 2 will examine the efficacy and feasibility of the proposed intervention using a randomized controlled design among 40 PWD/CG pairs. After baseline assessment, a 4-week, dyadic, hands-on, functionally-tailored oral care intervention will be delivered to 20 PWD/CG dyads. Control group participants (n=20) will receive the oral hygiene education that is commonly provided to PWD during dental care. Data collection will occur at baseline, 4-weeks and 3 months. Differences between the control and intervention groups with regard to PWD outcomes (e.g., oral hygiene and behavior symptoms during oral care), caregiver outcomes (e.g., burden, self-efficacy) and the care partner relationship will be explored.

This protocol has been developed to guide the study of Aim I and the Aim II study.

IV. Eligibility, Enrollment, and Consent

Sources of Recruitment. Tentatively, the study participants will be recruited from the sites listed below. The site names and IDs are as follows:

Table 2 recruitment sites and ID

Recruitment site	Site ID
Phase I study	10
Dementia registry	20
UI Memory Care Clinic ([name])	30
UI Dental School	40
UI Geriatric Clinic ([name]/[name])	50
Local Community (mass email)	60
UIHC list (TrinetX)	70
Mercy Caregiver Group	80
Huntington's Clinic	90
Mercy Center for Memory Health	11
Heritage Area Agency on Aging	12

Eligibility and Recruitment. 40 PWD/CG pairs will be recruited for the Aim 2 validation study. The eligibility criteria and recruitment strategies for both studies are the same. Recruitment letter will be mailed to the participants from site 10, 20, 40, 50 and 70. Approximately one week after mailing the letter, a member of the research team will contact the PWD or their legally authorized representatives (LARS). Recruitment material will also be distributed at site 30 and 50. A research team member will contact other participants from site 60 and 80 who expressed their interest to further explain the study and invite them to participate. All of the potential participants (PWD and FCG) will be screened according to the criteria below using *screening forms*.

The participant screening and recruitment form must be completed for ALL candidate participants who are approached for participation. All enrollments, refusals, withdrawn and excludes must be carefully documented for each approached PWD/CG and cross-checked among the recruitment sites.

PWD eligible for the study are those who meet the following criteria:

- 50 years of age or older 18 years or older with Huntington's Disease with a diagnosis of neurodegenerative disorder
- ≥1 natural teeth
- Not blind, deaf, or with severe physical disability (e.g., hemiplegia)
- English-speaking
- have a family CG who is age≥18, English-speaking, and willing to participate

PWD with the following condition will be excluded:

• Joint replacement with a history of prosthetic joint infection and/or that requires immediate dental referrals

- Oral health conditions (cancer, acute infection) that require an immediate dental referral
- Actively dying

The first seven conditions are included in the exclusionary criteria because the American Dental Association recommends antibiotic treatment prior to receiving dental care, which is not feasible in this study.

CG eligible for the study are those who meet the following criteria:

- Age≥18
- English-speaking

CG with the following conditions will be excluded:

- Cognitively impaired (based on 6-item cognitive screening tool);
- Blind, deaf, or severely disabled

Once eligibility is identified for both FCG and PWD, the research team member will ask if the dyad are self-responsible for consenting to research. If they are not, the research team member will ask for LAR contact information and proceed to contact the LAR, explain the study, and mail the informed consent to the LAR.

If dyad is self-responsible, prior to informed consent, the research assistant should evaluate the ability to provide informed consent of both PWD and FCG using The Evaluation to Sign an Informed Consent. If PWD, are deemed unable to consent, and have no designated LAR or POA, the research assistant should obtain written informed consent from the patient's next of kin in accordance with the UI IRB standard operating procedures for obtaining consent of human subjects with impairment in decision-making, specifically, in the order of spouse, adult child, siblings and relatives. Adequate time should be given for participants to process the information, and the research assistant should encourage participants to ask questions during the informed consent process.

Informed consent will be obtained from cognitively-intact caregivers using the protocol described above. If caregivers have legal guardians or power of attorney (POA), informed consent will be obtained from the responsible party. If the candidate caregivers are unable to consent and has no legal guardian or POA, the dyad will be excluded.

Either the self-responsible PWD, CG or his/her LAR will be asked to provide written informed consent

IV. Pilot study design Pilot study: was conducted December 2020 to March 2021

V. Stratification and Randomization

After informed consent, PWD will be assessed using the Dental Activities Test (DAT). Based on the DAT score, PWD and their FCG will be classified into 4 levels. Each level contains 10 dyads of PWD and FCG. All participants will be assigned to the intervention until we

reach 20 dyads then we will resume a control group. Each group has 5 dyads of PWD and FCG.

Table 3 Group assignment criteria

	9						
	Independent (DAT=9, N=10)	Needs Supervision (DAT=6-8, N=10)	Needs Assistance (DAT=3-5, N=10)	Full Care (DAT=0-2, N=10)			
Study group	5	5	5	5			
Control group	5	5	5	5			

VI. Oral Hygiene Intervention

Study group: a functionally-tailored oral care intervention will be provided to the dyads. The goal of the intervention is to improve oral hygiene for PWD while reducing the burden of the caregiver. Different modules will be combined to provide personalized oral care interventions for PWD and their FCGs based on their needs. The following table provides a general guide to develop an oral care intervention based on PWD's oral self-care function. Note that the intervention will need to be individualized based dyad's needs.

Table 4 Functionally Tailored Oral Care Interventions Corresponding to Dental Activities Test (DAT) Scores

(DAT) Scores								
		endent core 9)	Needs Supervision (DAT Score 6-8)		Needs Assistance (DAT Score 3-5)		Full Care (DAT Score 0-2)	
	PWD⁵	Caregive	PWD	Caregiver	PWD	Caregiver	PWD	Caregiver
Goals of intervention	1. Regain/ Maintai n function 2. Improve quality of self- care	1. Ensure quality of care	2. Improv e quality of self- care	1. Ensure oral care quality 2. Provide assistance to facilitate oral self- care		1. Provide assistance to facilitate oral care 2. Provide oral care as needed 3. Ensure quality of care 4. Manage behavior symptoms		1. Provide oral care 2. Ensure quality of care 3. Manage disruptive behaviors 4. Identify PWD in pain or infection
Common intervention								needs (module 8,
Personalize d Modules**	1, 2	1, 3	2	1, 3, 4	2	1 - 5	N/A	1 - 6

^{*} ACLs-Allen Cognitive Levels; § PWD-Persons with dementia; ** Module 1-Oral disease and impacts; 2-Oral care techniques; 3-Quality improvement; 4-Cuing strategies; 5-working with behavior symptoms; 6-Recognizing oral pain/infection.

The intervention will consist of 4 sessions. The OCC will first assess dyad's oral care needs in the first visit and then develop the intervention protocol with [name] based on the guidance listed in table 3. The goals and intervention tasks of each visit are summarized in the following table.

Table 4. Tentative Intervention Sessions and Contents for the Control Group

Visit	Goal	Intervention Sessions and Contents for the Control Group Intervention				
	- 7	Reviews intervention program				
		Deliver Module 1.1 and 3.1 to the dyad				
1	 Program overview Dyad education Goal identification Need assessment 	 Through dyad's demonstration, OCC assesses dyad's oral care skills (e.g., tooth brushing with disclosing solution and denture care, if applicable), preferences (e.g., floss vs. interdental brush), related challenges, and needs for adaptive oral hygiene products (specially-designed toothbrush, mouth prop) Assesses need for environmental changes (e.g., lighting, contrast, set-up of oral care products) Complete the rest of the items in the First visit assessment 				
000	develops function	form nally-tailored intervention plan to enhance what is currently				
		ng and compensate what needs to improve				
		Reviews intervention plan and materials				
	•Tooth brushing •Denture care (if applicable) •Interdental brushing •Dry mouth care	 Works with dyads to develop mutually agreed upon oral care plan (e.g., when and how often to perform oral care, use of oral care products) Module 2.0 				
		 Works with dyad to eliminate environmental obstacles Module 4.1 and other Modules and Scenarios as identified. 				
2		 Reviews personalized oral hygiene products (e.g., special toothbrush, toothpaste, or mouth prop) with dyad. 				
		Following the previously designed intervention plan, delivers hands-on, basic oral care (tooth brushing, denture care) and related skills training (e.g., cueing, quality improvement, behavior management as needed) via the trial & error strategy (tailor to dyad's needs and repeat until dyad demonstrates and fully learns the skills) Polivers delivered byginne long and instructions.				
		 Delivers daily oral hygiene logs and instructions. Review, discuss, and reinforce the basic skill set learned at the last visit. 				
		Review and reinforcement daily oral hygiene log				
3		 Review and reinforcement daily oral hygiene log Review oral care products required for interdental brushing, and dry mouth care. 				
		 Delivers training on cleaning between teeth, and dry mouth management. 				
		 Provide hand-on practice and real time feedback until dyads fully learn the skills. 				
	 Advanced skills reinforcement Program review, and wrap-up 	Reviews dyad's progress to date.				
		 OCC assesses and gives feedback of a dyad's final demonstration of oral care skills with disclosing solution. 				
4		 Review, discuss, and reinforce basic and advanced skill sets and tailor skills as needed. Discuss Modules that have not been reviewed, if necessary. 				
		Trainer and dyad work together to develop maintenance plan (with the minimum goal of once-a-day oral care)				

• Distributes the educational packet and resources for future use.

Control group:

Control group will have 3 visits: Initial visit, 4th week and F/U at 3 months. Control dyads will receive a 15-minute, home-based, untailored oral care training, using only Module 1 and Control Group OHI Module 2.7, in the first visit. After a demonstration, the OCC should allow participating dyads time to practice the oral care skills and provide real time feedback for the participants. After the demonstration, the1 Care recipient Feasibility Evaluation Questionnaire (if applicable) and the Caregiver Feasibility Evaluation questionnaire should be completed.

VII. Data Collection

[figure not shown]
Validation study.

The oral care coach (OCC) and research assistant (RA) will visit participants. The following data (Table 5.) needs to be collected during the validation study. Some of the data will be collected multiple times. Specifically, to avoid overburden to the study participants, the study coordinator should arrange an appointment before the intervention to collect all the baseline data. All the interviews and assessments should be given in a relaxed, comfortable environment and format. Breaks should be given if participants become tired, anxious or frustrated.

[figure not shown]
If a subject is identified as in need of immediate dental attention in the oral exam or during the intervention, the research assistant or OCC will document and communicate this need to the study coordinator. In accordance with approved IRB procedures and the data safety monitoring plan, the study coordinator will then send the consenting party a standardized notice recommending a follow-up examination. If needed, the identified issue will be reported to the IRB and the data safety monitoring committee.

[figure not shown]
The assessments should be given in the following order:

Visit 0

[figure not shown]
Visit 4

Visit 3-month

Dyad dy

^{*}if experimental group, collect and review oral care log before starting

Table 5. Data to be collected in the validation study

Data	Measure/Tool	Subject	Time	Examiner
Oral self-care function	Dental Activities Test (DAT)	PWD	Baseline	RA
Cognition	MMSE New cognitive screening tool (NCST) Mini-Cog	PWD	Baseline	RA
Daily function	ADL and IADL	FCG	Baseline	RA
Depression	Visual analogue scaleCESD depression scale	PWD	Baseline	RA
Apathy	Dementia Apathy Interview and Rating	FCG	Baseline	RA
Anosognosia	AnosognosiaSelf-perceived oral health	PWD/FCG	Baseline	RA
Oral hygiene	Plaque index Gingival index	PWD	Baseline 4-week follow-up 3-month follow-up	Dentist
 Sociodemographics Medical history & medication Dental care pattern 	Caregiver Interview	FCG	Baseline	RA OCC
 Oral hygiene practice Perceived oral hygiene and oral health Behavior symptoms during oral care Mouth Care Related Caregiver Burden Dyadic relationship 	Caregiver Interview	FCG	Baseline4-week follow-up3-month follow-up	LD &RA
CG efficacy in providing oral care	Caregiver Self-efficacy Scale	FCG	Baseline4-weekfollow-up3-monthfollow-up	RA
First visit assessment	First visit assessment form	PWD/FCG	1 st visit	LD
Feasibility assessment (session)	 Care recipient Feasibility Evaluation Questionnaire Caregiver Feasibility Evaluation Questionnaire 	PWD/FCG	Every session	LDRA
Trainer assessment	Trainer evaluation questionnaire	Trainer	Every session	LD
Daily oral care practice	Daily oral care log	PWD/FCG	Every session3-month follow-up	LD

Feasibility assessment (program)	•	Care recipient Program Feasibility Evaluation Questionnaire Caregiver Feasibility Program Evaluation Questionnaire	PWD/FCG	4-week follow-up	RA
Implementation assessment	•	Training log & trainer interview	Trainer	Every session	XC

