**Document date: 02-17-2023** 

## Statistical Analysis Plan

First, descriptive statistics were calculated to describe the characteristics of the study participants at baseline, 4-week follow-up, and 3-month follow-up. Wilcoxon rank-sum tests were used to compare continuous/numeric variables between the control and intervention groups at each visit. Fisher's exact tests were used to compare categorical variables. No adjustments have been made for multiple comparisons. After that, Wilcoxon rank-sum tests were used to compare percent and raw score change in the primary outcomes between baseline and 4 weeks and baseline and 3 months in the study and control groups.

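### Aim 2 is labelled randomised, but the only allocation rule given is sequential and predetermined: state how each dyad was assigned and make the label match

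*Protocol*

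**What the plan says.** Protocol, III. Project Overview: Aim 2 "will examine the efficacy and feasibility of the proposed intervention using a randomized controlled design among 40 PWD/CG pairs". The same section says that differences between the groups in patient and "caregiver outcomes (e.g., burden, self-efficacy) and the care partner relationship will be explored".

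Protocol, V. Stratification and Randomization: after consent and the DAT, dyads are classified into four levels of 10. The assignment rule follows: "All participants will be assigned to the intervention until we" "reach 20 dyads then we will resume a control group". Then: "Each group has 5 dyads of PWD and FCG". Table 3 gives the target counts, 5 study and 5 control dyads in each level. The section describes no random sequence, block scheme, concealment or person who assigns.

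Protocol, IV. Eligibility, Enrollment, and Consent, on screening records: "All enrollments, refusals, withdrawn and excludes must be carefully documented for each approached PWD/CG and cross-checked among the recruitment sites".

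SAP, Statistical Analysis Plan: "Wilcoxon rank-sum tests were used to compare continuous/numeric variables between the control and intervention groups at each visit". Categorical variables are compared with Fisher's exact test, and percent and raw change in the primary outcomes with Wilcoxon tests. The text available has no term for enrolment period or DAT level and does not mention allocation. It is written in the past tense.

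**The concern.** The label and the rule describe different designs. In a randomised comparison chance decides the arm, so time trends and recruiters' choices fall on both arms alike. Under the written rule the enrolment count decides the arm. Three things can then enter the comparison:

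- **Calendar trends**, for example in coaching practice or examiner scoring.
- **Changes in recruitment source.** Protocol Table 2 lists eleven sources, described as tentative, from a memory clinic and a dental school to a Huntington's clinic and an agency on aging.
- **Selective enrolment.** Staff who approach and screen dyads could know the next arm before screening if the count is overall, or at the latest once the DAT is scored if it runs within level.

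At stake is how a between-arm p-value is read. The Overview pairs efficacy with a randomised design, so a reader would take it as randomised evidence. Feasibility outcomes do not depend on comparable arms and are not affected.

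**Working it through.** **1. The plan's counts.** Four levels × 10 = 40 dyads; four levels × 5 = 20 per arm. Both agree with the Overview. The counts are consistent; the problem is the mechanism.

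**2. What the rule allows.** For a given enrolment order, the written rule permits exactly one assignment. Random 5/5 assignment within each level would permit C(10,5)^4 = 252^4 = 4,032,758,016. Table 3 gives target cell sizes and supplies no chance element.

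**3. Overall count or within level?** The text does not say. If the first 20 dyads overall go to intervention and 10 dyads per level arrive in random order, the chance that those 20 split 5/5/5/5 is 252^4 / C(40,20) = 4,032,758,016 / 137,846,528,820 = 0.029. An overall count therefore would not by itself deliver Table 3. A cap of 5 per level would, but arm would still be predetermined.

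**4. How closely arm follows order.** Suppose c controls came first, then 20 intervention dyads, then 20 − c controls. The mean enrolment position is c + 10.5 for intervention and 30.5 − c for control, a difference of 20 − 2c. The SD of positions 1 to 40 is √((40² − 1)/12) = 11.54. Hence |r| = 0.5 × (20 − 2c) / 11.54:

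- c = 0: 10 / 11.54 = 0.87
- c = 6: 4 / 11.54 = 0.35
- c = 10: 0

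Under the within-level reading with random arrival and no earlier controls, simulation gives a mean |r| of 0.81.

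**5. Illustration of consequence.** Assumptions, none from the documents: normal outcome, no treatment effect, one step shift in the analysed outcome, 20 v 20 Wilcoxon, two-sided 5%. The spurious arm difference is the step times the difference between arms in the share of dyads enrolled after it. For a step after dyad 20 that is step × (20 − 2c)/20.

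| Earlier controls c | Step (SD) | Spurious difference (SD) | False positives |
|---|---|---|---|
| 0 | 0.2 | 0.2 × 1.0 = 0.20 | about 9% |
| 0 | 0.5 | 0.5 × 1.0 = 0.50 | about 32% |
| 6 | 0.2 | 0.2 × 0.4 = 0.08 | about 6% |
| 6 | 0.5 | 0.5 × 0.4 = 0.20 | about 8% |

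The within-level reading with a 0.5 SD midway step gives about 21%.

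The midway step is the worst case when c = 0. A 0.5 SD step after dyad 30 gives a spurious difference of 0.5 × 10/20 = 0.25 SD and about 11% for every c from 0 to 10, since the last 10 dyads are then all controls. A low order correlation is therefore not full protection: at c = 10 it is zero, yet a 0.5 SD step after dyad 10 also gives about 11%.

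**6. Which tests are exposed.** A stable additive shift between early and late enrollees cancels in raw change from baseline. It does not cancel in the per-visit comparisons, nor fully in percent change. A shift in the change itself affects all of them.

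**The case against.** **Some dyads may have been randomised.** *Resume* implies that control assignment had begun before the rule, possibly at random. Part of the SAP was not available and figures are missing, so a random procedure described elsewhere cannot be excluded. This stands. A reader might infer that the trial as run was wholly non-randomised; the documents do not show that. They show that the label and the only stated rule conflict. For the same reason a blanket non-randomised label could be false for a concurrently randomised subset.

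**The study is small and exploratory.** The Overview does say that differences will be explored. A reader might also infer that sequential allocation leaves no evidence of efficacy at all. That goes too far: it weakens causal inference, and a separately analysed randomised subset would keep its standing. But the exploratory wording does not correct the design label, which stands beside a stated aim of examining efficacy.

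**The simulated shifts are invented.** They are, and 32% combines the least favourable order, timing and larger step. At 0.2 SD, or with earlier controls, the inflation is modest. The conflict between label and rule does not depend on any simulation.

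**Conclusion.** The point holds as a conflict between label and rule, and it should be corrected before any between-arm result is reported. Confidence is high that the text contradicts itself; it is not high on whether the trial as run was non-randomised. For dyads assigned by the written rule, arm follows enrolment order and is foreseeable under either reading of it, so the SAP's unadjusted comparisons of those dyads are open to period confounding and selective enrolment. The size in this trial is unknown. It depends on how many dyads were assigned before the rule and how, and on whether outcomes or recruitment sources drifted; the documents give neither. The false-positive rates above show a range under assumed shifts and are not estimates for this trial.

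**What to change.** 1. State how and when each dyad was assigned, including any phase before the sequential rule, the date of any switch, and whether the rule ran overall or within DAT level.
2. Label each phase accordingly. Keep the randomised label only for dyads assigned by a documented random procedure, describe the rest as non-randomised sequential allocation, and change the Project Overview and section V to match.
3. If a subset was concurrently randomised, identify it and analyse it separately as the randomised comparison.
4. Add to the SAP that any between-arm comparison including sequentially allocated dyads is non-randomised and exploratory, with possible confounding by enrolment period.
5. Report recruitment site by arm, and enrolment dates by arm where recorded. Report refusals and exclusions before and after the switch if the screening records carry dates; section IV requires the records but does not mention dates.

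Cost: a short account of assignment, wording changes in two places, one SAP sentence and one table, plus a separate analysis if a randomised subset exists. No extra participants are needed.

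Only if allocation has not begun, which the past-tense SAP makes unlikely, use concealed 1:1 randomisation within DAT level to the Table 3 counts. That needs an allocation list and a short amendment, with 40 dyads unchanged. With one block of 10 per level, staff who track allocations could guess on average 5 + (2^10/252 − 1)/2 = 6.5 of 10 assignments, against 5 by chance, and would know the last 10/6 = 1.7 with certainty.

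### Arms are filled in enrolment order, not at random; the rule does not ensure the 5-per-DAT-level layout, and the SAP adjusts for neither DAT level nor enrolment period

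*Protocol*

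**What the plan says.** The Protocol's Project Overview (Section III) says that Aim 2 will be studied "using a randomized controlled design among 40 PWD/CG pairs", with 20 dyads in each arm.

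Section V, headed Stratification and Randomization, has the DAT scored after consent and sorts dyads into four levels of oral self-care function. It then makes two kinds of statement:

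- **A target layout.** "Each level contains 10 dyads of PWD and FCG", and Table 3 shows 5 study and 5 control dyads in each level.
- **An operating rule.** Every dyad goes to the intervention at first, and the arm changes on the overall count, once recruiters "reach 20 dyads then we will resume a control group. Each group has 5 dyads of PWD and FCG".

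The section describes no random sequence and no concealment of allocation. It does not say what happens to a sixth dyad of one level while the intervention arm is still filling.

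The SAP applies Wilcoxon rank-sum and Fisher's exact tests "between the control and intervention groups at each visit", then rank-sum tests of raw and percent change from baseline in the primary outcomes. It names no stratification, covariate or term for enrolment period.

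**The concern.** There are two problems, and the first is the firmer.

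**Allocation is by order, not by chance.** The first 20 dyads are intervention and the rest control. The next dyad's arm is always known, so who is approached, and when, can depend on it. Arm also coincides with anything that changes over recruitment: season, the mix of the eleven recruitment sources in Table 2, and the experience of the oral care coach and examiners. The name of the section and the description of the design promise protection that this rule does not give.

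**The rule is not tied to the DAT layout.** It changes arm on the overall count, whereas Table 3 needs a change within each level. DAT level determines which modules an intervention dyad receives (Section VI, the table of tailored interventions), and managing behaviour appears among the goals only at the lower levels. Behaviour symptoms and caregiver burden are also outcomes. If the arms differ in DAT mix, part of an observed difference could reflect function rather than the intervention.

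**Working it through.** **1. The plan's own figures.** Table 3: 4 levels × 10 dyads = 40; 4 × 5 = 20 per arm. These agree with the overview. The documents give no power calculation to reproduce.

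**2. Does the rule by itself produce Table 3?** Assume exactly 10 dyads per level, random arrival order and no cap per arm within a level. The first 20 dyads are then a random half of the 40:

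P(5/5/5/5) = C(10,5)^4 / C(40,20) = 252^4 / 137,846,528,820 = 4,032,758,016 / 137,846,528,820 = 0.029.

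Full enumeration gives the worst departure from 5 in any level:

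| Worst split in any level | Probability |
|---|---|
| 5:5 | 2.9% |
| 6:4 | 32.8% |
| 7:3 | 43.1% |
| 8:2 | 17.9% |
| 9:1 | 3.0% |
| 10:0 | 0.2% |

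7:3 or worse: 43.1 + 17.9 + 3.0 + 0.2 = 64.2%. 8:2 or worse: 17.9 + 3.0 + 0.2 = 21.1%.

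Without level quotas, the chance that the first 20 are 5/5/5/5 is 20!/(5!)^4 × (1/4)^20 = 0.011 if levels are equally common (assumption), and 0.0009 if they occur as 40/30/20/10% (assumption).

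**3. What if a cap of 5 per level per arm is applied?** Table 3 is then met exactly, provided recruitment fills every cell. The tie to enrolment order remains:

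- If control opens only after 20, intervention dyads hold places 1 to 20 (mean 10.5) and control dyads 21 to 40 (mean 30.5), a gap of 20 places.
- If control opens level by level, with levels equally common (assumption), simulation gives a mean gap of about 17 places out of 40.

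**4. Could DAT imbalance mislead the unadjusted test?** Simulation of 2,000 trials per setting, with no treatment effect, no cap, and an outcome that shifts 0.5 SD per DAT level. The slope and the drift are assumptions. Moderate drift means that the level mix moves from 40/30/20/10% at the first dyad to 10/20/30/40% at the last.

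| Drift in level mix | Mean level difference between arms | False-positive rate at 0.05 |
|---|---|---|
| None | about 0 | 0.05 |
| Mild | −0.26 | 0.05 |
| Moderate | −0.50 | 0.11 |
| Strong | −0.76 | 0.18 |

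Under the same slope, with Table 3 met exactly, the unstratified test rejects in only 0.023 of trials. It is then conservative, so using DAT level in the analysis has value even when the arms are balanced.

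**The case against.** A reader might infer that the rule cannot deliver Table 3 and that function level is therefore confounded with arm. The documents support neither step.

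- **Table 3 is attainable.** The DAT is scored before assignment and the quotas are stated. Sending the first 5 dyads of each level to intervention and the next 5 to control gives the required cells. It meets the 20-dyad rule strictly if all intervention cells fill before control opens. What stands is that the protocol does not state this procedure. Under the model in step 2 of the working, 100 − 2.9 = about 97% of arrival orders bring a sixth dyad of some level before the intervention arm is full. Staff must then overfill the cell, open control early or hold the dyad back, and the protocol provides for none of these.
- **Imbalance need not be bias.** With random arrival order, the spread of DAT splits is the same as under unstratified randomization of these 40 dyads into two arms of 20. The expected difference is zero and the false-positive rate stays near 0.05. Systematic confounding by DAT needs a drift in level mix, and the documents give no evidence of drift either way.
- **The SAP gives some protection.** Raw change from baseline removes a stable additive difference between levels, and percent change a stable proportional one. Baseline comparisons could reveal an imbalance in DAT. Neither handles a response that differs by level, and neither addresses enrolment period. The false-positive rates above concern outcome levels at a visit and should not be read across to the change scores.

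It is also fair to say that this is a 40-dyad study of efficacy and feasibility whose group differences are to be explored. That lowers the stakes, but it does not make the allocation random.

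**Conclusion.** The point stands in this form: allocation is sequential, which contradicts the randomized design claimed in the overview; the means of reaching 5 dyads per level per arm is not stated; and the SAP adjusts for neither DAT level nor enrolment period.

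The contradiction rests on the text alone. The figures of about 3% and 64% hold only with 10 dyads per level, random arrival order and no per-arm cap. With a cap and full recruitment the layout is met with certainty. Harm from DAT imbalance is possible but not shown: beyond chance it depends on drift and on a DAT–outcome relation, and the documents quantify neither. The tie between arm and enrolment time holds on either reading, and DAT adjustment cannot remove it.

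The word *resume* may tempt a reader to infer that some dyads were allocated under a different scheme before this rule. The documents do not say so.

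**What to change.** **If enrolment is open:** allocate the dyads still to be assigned at random, from a concealed list of permuted blocks within each DAT level (5 study, 5 control), and close a level at 10. This secures Table 3 and breaks the tie to enrolment order. Dyads already assigned in sequence stay non-randomized and should be reported as such. Cost: an allocation list and a few sentences of protocol text; filling rarer levels may slow recruitment.

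**If enrolment is complete,** as the SAP's past tense suggests though neither document says so:

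1. Describe the allocation as sequential and non-randomized wherever the design is named.
2. Report the actual DAT-by-arm table, and drop the 5-per-cell statement if it was not met.
3. Stratify the primary comparisons by DAT level (van Elteren test) or include DAT as a covariate.
4. State that this does not remove confounding with enrolment period.

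Cost: a few sentences and one further analysis. Very unequal cells contribute little to a stratified test, and a level with an empty arm contributes nothing.
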